4.0 Introduction

This statistical analysis plan (SAP) provides a detailed elaboration of the statistical analyses of the efficacy and safety data as specified in the final protocol of Study 1925-201-008 (amendment 1 version dated 25 September 2020). Specifications of tables, figures, and data listings are contained in a separate document.

This is a phase 2, multi-center, randomized, double-blind, placebo-controlled, dose-ranging study in patients 55-90 years of age who are scheduled to undergo open-chest cardiac surgery.

The length of this study will be 367 days, not including the screening visit, which may occur up to 28 days before the first study day (randomization). Signed informed consent from the participant will be obtained before any study-related procedures are begun. Patients meeting the inclusion/exclusion criteria will be randomized (1:1:1 ratio) to one of three treatment arms at the end of the screening period. Primary and secondary efficacy assessments will be assessed for 30 days post-surgery. Additional efficacy and exploratory assessments will be assessed through Day 367 post-surgery. All participants will be followed through Day 367 for safety assessments. Every attempt will be made for participants who prematurely discontinue from the study, regardless of cause, to be seen for a final evaluation.

The study schema is presented below.

D = study day; TC = telephone call; U = units; V = Visit

a Hospital discharge could take more than 6 days.

The schedule of evaluations is presented in the Table 4–1 below.

Page 7

Table 4–1Schedule of Evaluations: Study 1925-201-008

Study Period	Screening ^a	Days 1 to 60						Day 61 through Day 360								
Visit Number	V1	V2	V3	V4 ^b	V5 ^b	V6 ^b	V7 ^b	TC1	V8	V9	V10	V11	V12	V13	TC2	Early
Day Number	(up to 28 days)	D1	D2	D3	D4	D5	D6	D14	D30	D60	D90	D180	D270	D360	D367 ^d	Disc
Visit Windows	-	-	-	-	-	-	-	± 3d	± 3d	± 3d	± 7d	± 7d	± 7d	± 7d	V13 + 7d (+ 7d)	-
Informed consent	Х															
Inclusion and exclusion criteria	Xe	Х														
Demography	Х															
Physical examination	Х								Х					Xf		Х
Medical history	X															
Urine pregnancy test (for women of childbearing potential) ^{e,g}	Х	x														
Laboratory assessments ^{e,h}	Х	Х					Х		Х	Xi	Xi			Xi		Х
Sample collection for biomarker assessment ^e		Х	х	Х	Х											
12-lead ECG ^j	Х	Х	Х	Х	Х	Х	Х		Х	Xk	Xk	Xk	Xk	Xk		Х
ECG patch		Х	Х	Х	Х	Х	Х	Х	X ¹	X ^m	Х					
Vital signs ^{e,n}	Х	Х	Х	Х	Х	Х	Х		Х	Х	Х	Х	Х	Х		Х

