10.3 Additional Efficacy Variables

Hospital and ICU Length of Stay

Hospital length of stay for the initial care of indication under study is defined as the time (days) from ICU admission date/time to the date/time of discharge from the hospital. ICU length of stay is defined as the time (hours) from the ICU admission date/time to the date/time of discharge from the ICU. For participants not admitted to the ICU, ICU length of stay will be set to zero and hospital length of stay will be defined as the time (days) from end date/time of study drug administration to date/time of discharge from hospital. For subjects missing ICU admission date/time, ICU admission date/time will be imputed to the end date/time of study drug administration. The date/time of death will be used to derive hospital length of stay for participants who died at the hospital (and ICU length of stay, for participants who die in the ICU).

Descriptive statistics (n, mean, SD, Q1, median, Q3, min, max) for hospital and ICU length of stay will be presented by:

- treatment group
- region (U.S. versus non-U.S.) and treatment group
- country and treatment group
- sites and treatment group

Between-group treatment comparisons in hospital and ICU length of stay will be performed for each AGN-151607 treatment arm versus placebo using the following methods:

- An ANOVA model with treatment group, type of surgery, age group, and region as factors
- An ANOVA model with treatment group and region as factors
- An ANOVA model with treatment group and country as factors

- A stratified Wilcoxon (Van Elteren) test, stratified by type of surgery, age group, and region
- A stratified Wilcoxon (Van Elteren) test, stratified by type of surgery and age group

Descriptive statistics of hospital length of stay measured from the time of initial hospital admission to discharge will be presented by:

- treatment group
- region (U.S. versus non-U.S.) and treatment group
- country and treatment group
- sites and treatment group

ANOVA models, as described above, will be used to estimate confidence intervals for difference in mean hospital length of stay measured from the time of initial hospital admission between each AGN-151607 treatment arm and placebo.

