17.0 Version History

DOCUMENT HISTORY

Document	Date	
Original Final Analysis Plan	26 Apr 2021	
Amendment 1	19 Nov 2021	
Amendment 2	31 May 2022	

Table 17–1Final Analysis Plan Version History Summary

Amendment	Date	Summary	
	26 Apr 2021	Original version	
1	19 Nov 2021	• Added supplementary analyses using Supplementary ePatch Analysis Sets described in Sections 6.3, Section 10.1 and Section 10.2;	

Amendment	Date	Summary	
		• Added list of antiarrythmics and concurrent procedures due to atrial fibrillation or atrial flutter to Section 8.0;	
		• Edited so that mis-stratified participants, if any, will be analyzed based on the correct stratification group in Section 10.0;	
		• Added percentage of patients at least 1 continuous AF episode ≥ 6 minutes during the first 30 days post-surgery as a secondary efficacy variable in Section 10.0 and Section 10.2;	
		• Clarified definition of "symptomatic AF" in Section 10.2;	
		• Added Cox proportional hazards models as additional analyses for time-to- event endpoints in Section 10.2;	
		• Added imputation rules for missing ICU admission date/times in Section 10.3;	
		• Added stratified Wilcoxon (Van Elteren) tests for length of stay endpoints in Section 10.3;	
		• Added hospital length of stay measured from the time of initial hospital admission to discharge as an endpoint in Section 10.3;	
		• Added clarification for Poisson regression model and an additional analysis using total analyzed time in the model in Section 10.3;	
		• Added components to the composite endpoint, specified binary and time- to-event versions, and clarified definitions of terms for the Win Ratio analysis in Section 10.3;	
		• Added changes to analyses specified in protocol in Section 16.0.	
2	31 May 2022	• Added supplementary analyses using Beta Blocking Agent Withdrawn ePatch Analysis Set, described in Sections 6.4 and Section 10.1;	
		• Clarified that calculation of time spent in AF (AF burden) will exclude continuous AF episodes < 30 seconds in duration in Section 10.2;	
		• Added restricted mean survival time (RMST) to time-to-event analyses described in Section 10.2;	
		• Added negative binomial, zero-inflated negative binomial and zero-inflated Poisson models to analysis of number of AF events in Section 10.3;	
		• Added 'Percentage of participants free from AF through 12 months post- surgery and not taking any anticoagulant drugs' as Additional Efficacy variable in Section 10.3;	

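### The confidence intervals for admission-to-discharge hospital stay in SAP 10.3 are valid but wider than needed, because days in hospital before study drug are not used as a covariate.

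*SAP*

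**What the plan says.** SAP 10.3 has two versions of hospital length of stay for the index surgery.

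- The main version is "defined as the time (days) from ICU admission date/time to the date/time of discharge from the hospital", or runs from the end of study-drug administration for participants who do not go to the ICU. It is compared between each dose and placebo by three ANOVA models and two Van Elteren tests.
- The second version starts at initial hospital admission. SAP 17.0 records it under Amendment 1: "Added hospital length of stay measured from the time of initial hospital admission to discharge as an endpoint in Section 10.3". It receives descriptive statistics, and then "ANOVA models, as described above, will be used to estimate confidence intervals" for the "difference in mean hospital length of stay measured from the time of initial hospital admission between each AGN-151607 treatment arm and placebo". No rank test is planned for it.

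The three models referred to are:

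1. "An ANOVA model with treatment group, type of surgery, age group, and region as factors"
2. "An ANOVA model with treatment group and region as factors"
3. "An ANOVA model with treatment group and country as factors"

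None contains the time in hospital before surgery. On timing, the protocol synopsis places randomization on Day 1 and the injections during the operation.

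**The concern.** Stay from admission to discharge is the sum of a part before study drug and a part after it. The drug cannot act on the first part. That part adds variance to the outcome but no treatment effect, and it is known for every participant before dosing. Such a variable belongs in the model as a baseline covariate. The SAP does this elsewhere: the quality-of-life models in SAP 10.4.2 include the baseline score.

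What is at stake is precision. The reported interval for total stay carries avoidable noise whenever pre-operative stay varies within a region or country.

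**Working it through.** **Inputs.** The documents give no planning SD, precision target or power for any length-of-stay comparison, so there is no figure of the plan's own to reproduce here. The number per arm, 100, comes from SAP 13.0. All SDs and correlations below are assumptions, shown as ranges.

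**Formulas.** Let SDpre and SDpost be the SDs of pre- and post-operative days, and r their correlation.

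- Residual variance without the covariate: SDpost² + SDpre² + 2·r·SDpre·SDpost
- Residual variance with the covariate: SDpost²·(1 − r²)
- Difference between the two: (1 + b)²·SDpre², where b = r·SDpost/SDpre is the slope of post-operative on pre-operative days
- 95% half-width: 1.96 × residual SD × √(2/100)

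The difference is never negative. It is zero only if SDpre = 0 or b = −1. Apart from one degree of freedom, the covariate therefore cannot widen the interval.

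**Zero correlation.** With the covariate the half-width is 1.96 × 4 × √(2/100) = 1.11 days for SDpost 4, and 1.66 days for SDpost 6. Without it:

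| SDpre (days) | Half-width, SDpost 4 | Excess | Half-width, SDpost 6 | Excess |
|---|---|---|---|---|
| 1 | 1.14 | 3% | 1.69 | 1% |
| 2 | 1.24 | 12% | 1.75 | 5% |
| 3 | 1.39 | 25% | 1.86 | 12% |
| 4 | 1.57 | 41% | 2.00 | 20% |

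For example, with SDpost 4 and SDpre 3 the ratio is √(16 + 9)/4 = 1.25. The variance ratios for SDpost 4 are 17/16, 20/16, 25/16 and 32/16. They equate to needing 6%, 25%, 56% or 100% more participants for the same width.

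**Non-zero correlation.**

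- At r = +0.2 and SDpost 4, the excess is 10%, 23%, 39% or 58% for SDpre 1 to 4.
- At r = −0.2 and SDpost 5, the adjusted SD is 5 × √0.96 = 4.90. The unadjusted SDs are √24, √25, √28 and √33, so the excess is 0%, 2%, 8% or 17%. The zero arises because b = −0.2 × 5/1 = −1.

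**Allowing for region.** The formulas above ignore the other model terms. Model 1 was simulated with 100 per arm, a skewed post-operative stay with SD about 4, a two-level region, and 60 runs per setting. The excess was:

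| Share of pre-operative variance between regions | SDpre 1 | SDpre 2 | SDpre 3 | SDpre 4 |
|---|---|---|---|---|
| None | 3% | 11% | 24% | 38% |
| 30% | 2% | 7% | 16% | 30% |
| 60% | 1% | 5% | 10% | 16% |

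**Chance imbalance.** The 95% range for the arm difference in mean pre-operative days is ±1.96 × SDpre × √(2/100), which is ±0.55 days for SDpre 2 and ±0.83 days for SDpre 3. The unadjusted interval already allows for this, which is part of why it is wider.

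**The case against.** The strongest reply is that the SAP already has the precise analysis. The main length-of-stay comparison starts at ICU admission, so it excludes the pre-operative days and gets the fuller set of tests. In a linear model, regressing total stay on treatment and pre-treatment days gives the same treatment coefficient as regressing post-treatment stay on those terms. The adjusted result would thus largely repeat the ICU-based one. Total stay also has a use of its own as a resource measure: protocol 8.9 lists total days in hospital among the health-economic data. This limits the importance of the point but does not remove it. The SAP still reports a separate interval for total stay, and the covariate narrows it without changing what is estimated.

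A second reply also stands in part. Every one of the models has region or country as a factor, so differences in admission practice at that level are already removed. Only variation within region or country widens the interval.

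Two stronger readings are tempting, and the documents support neither.

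- A reader might infer that an imbalance in waiting time would be passed off as a drug effect. These days precede dosing, so randomization balances them in expectation, and the interval covers the chance imbalance that remains.
- A reader might take the 28-day screening window in SAP 4.0 as showing long pre-operative stays. That window concerns the screening visit, not inpatient time. The schedule of activities allows screening and randomization on the same day, participants are scheduled for surgery, and emergency surgery is excluded.

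**Conclusion.** The point holds as a loss of precision only. The admission-to-discharge estimate is unbiased and its interval keeps its coverage, but the interval is wider than needed.

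The direction follows from the algebra. The size rests wholly on assumed SDs and correlations. The zero-correlation range is about 1% to 41%. A large between-region share or a modest negative correlation brings the upper end down to 16% or 17%, while a positive correlation raises it. If nearly everyone is admitted the day before surgery or on the day itself, the loss is negligible.

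The consequence for the trial is minor. This is an additional efficacy variable, SAP 10.0 applies no multiplicity adjustment to it, and the ICU-admission-based comparison beside it is unaffected.

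**What to change.** In SAP 10.3, add days from hospital admission to study-drug administration as a continuous covariate in each ANOVA model for admission-to-discharge stay. Summarise those days by arm, for example with the baseline characteristics in SAP 8.0, so that readers can see any imbalance.

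The cost is one model term and one summary row. The admission time is already needed for this endpoint, and SAP 10.3 already uses the end date and time of study-drug administration. The expected arm difference in total stay is unchanged, and the ICU-admission-based analyses need no change.

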#### CONFIDENTIAL

#### AGN-151607

Study Period	Screening a				D	ays 1 to	60					Day 61	through l	Day 360		
Visit Number	V1	V2	V3	V4 b	V5 b	V6 b	V7 b	TC1	V8	V9	V10	V11	V12	V13	TC2	Early
Day Number	(up to 28 days)	D1	D2	D3	D4	D5	D6	D14	D30	D60	D90	D180	D270	D360	D367 d	Disc e
Visit Windows	-	-	-	-	-	-	-	$\pm 3d$	$\pm 3d$	$\pm 3d$	$\pm 7d$	$\pm 7d$	$\pm 7d$	$\pm 7d$	V13 + 7d (+ 7d)	-
AFEQT	Х								Х		Х	Х				Xs
AFSS	Х								Х		Х	Х				Xs
DASI	Х								Х		Х	Х				Xs
EuroSCORE IIt	Х															
SF-12v2	Х								Х		Х	Х				Xs
EQ-5D-5L	Х								Х		Х	Х				Xs
Record discharge from ICU		Х	Х	Х	Х	Х	Х									
Record discharge from hospital			Х	Х	Х	Х	Х									
Record any additional healthcare resource utilization								Х	Х	Х	Х	Х	Х	Х	X	Х
Serum sampling for immunogenicity assessment u	X								Х		Х					

AE = adverse event; AF = atrial fibrillation; AFEQT = Atrial Fibrillation Effect on Quality-of-life Questionnaire; AFSS = University of Toronto Atrial Fibrillation Severity Scale; D(d) = day; DASI = Duke Activity Status Index; Disc = discontinuation; ECG = electrocardiogram; EQ-5D-5L = A measure of health-related quality of life developed by the EuroQol Group; FU = follow-up; ICU = intensive care unit; PFT = pulmonary function test; SAE = serious adverse event; SF-12v2 = Short Form-12 Health Survey, version 2; TC = telephone call; V = visit

a Screening and randomization activities can occur on the same day. If screening and randomization occur on the same day, all assessments for Visit 1 and Visit 2 should be completed. Duplicate assessments (eg, laboratory assessments) do not have to be completed twice; please note a 12-lead ECG is required both before and after surgery.

b These visits are optional and are only required if the participant is still hospitalized. Participants may remain in the hospital beyond Day 6, based on the recovery from surgery. The study visit procedures will have to be performed each day until discharge.

c In case of early discontinuation, attempts will be made to follow-up with the participant.

d Day 367 must be at least 7 days and should be no more than 14 days after Visit 13 (Day 360).

e On Day 1, assessments to be performed prior to surgery.

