9.0 Extent of Exposure

All study participants will be treated only once on their day of surgery. Study treatment exposure data will be listed for the safety population.

Descriptive statistics of the study duration, calculated for each participant as the number of days from the date of the study treatment to the date the participant exits the study, will be presented by treatment group. In addition, the number and percentage of participants whose study duration belong to each of the following intervals will also be presented by treatment group: ≥ 6 days, ≥ 14 days, ≥ 30 days, ≥ 60 days, ≥ 90 days, ≥ 180 days ≥ 270 days, ≥ 360 days. These summaries will be based on the safety population.

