Descriptive statistics of number of days spent in the hospital within 30 days post-discharge and within 60 days post-surgery will be presented by treatment group. Summary statistics will also be presented by treatment group for the reasons for hospital and ICU admissions.

Rehospitalization within 30 Days Post-Discharge and 60 Days Post-Surgery

The percentage of participants with at least one all-cause rehospitalization within 30 days postdischarge and percentage of participants with at least one all-cause rehospitalization 60 days post-surgery will each be presented by treatment group. Similar summaries will be presented for non-arrhythmia cardiovascular rehospitalization and arrhythmia cardiovascular rehospitalization. These variables will be analyzed using the same method presented for the primary efficacy variable in Section 10.1. Descriptive statistics of the total number of rehospitalizations within 30 days post-discharge and 60 days post-surgery as well as the length of rehospitalization stay will also be presented by treatment group for each of the different causes of rehospitalizations (allcause, non-arrhythmia cardiovascular and arrhythmia cardiovascular).

The time (days) to the first all-cause rehospitalization will be calculated as the date/time of first re-hospitalization minus the date/time of hospital discharge after surgery. This will be analyzed using the KM method discussed in Section 10.2. Participants with no rehospitalizations will be censored at their respective study exit day. Similar analyses will be performed for non-arrhythmia cardiovascular rehospitalization and arrhythmia rehospitalizations.

Healthcare Resource Utilization within 30 Days, 60 Days, and 365 days Post-Discharge

The proportion of participants with any healthcare resource utilization (outside of any planned in-patient hospitalization, procedures and medications) within 30 days, 60 days, and 365 days post-discharge will be presented by treatment group. The type of resource utilized (e.g., Outpatient hospital, Physician's office, etc.) as well as the reason for the visit will also be tabulated in a similar manner. Descriptive statistics of the number of times each participant utilizes a healthcare resource within each of the specified timeframe will also be presented by treatment group. Note that any unplanned inpatient hospitalization will also be included in these summaries.

Need for Medical or Procedural Intervention Due to AF

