The following five binary (yes/no) variables will be used to analyze the need for pharmacologic and/or procedural intervention due to AF during the first 30 days post-surgery:

- 1. at least one pharmacologic intervention (i.e., anticoagulation or antiarrhythmic drugs)?
- 2. at least one anticoagulation pharmacologic intervention?
- 3. at least one antiarrhythmic pharmacologic intervention?
- 4. at least one procedural intervention (see list in Section 8.0)?
- 5. at least one pharmacologic or procedural intervention?

In addition, time to event variables will also be created for each of the corresponding 5 variables above. The time to the first event will be used for analysis. All these variables will be analyzed using the same methods for similar variables in Sections 10.1 and 10.2.

The need for pharmacologic and/or procedural intervention due to AF from Day 31 to Day 360 post-surgery will be analyzed in a similar fashion. Participants with no events who exit the study prior to Day 360 will be censored at their respective study exit day minus 30 days, while participants with no events who exit the study on or beyond day 360 will be censored at day 330 (360 - 30 = 330). Pharmacologic and/or procedural interventions due to AF with onset dates prior to day 31 that are ongoing at day 31 will count as events for these endpoints, with a time-to-event equal to zero.

Descriptive statistics will be presented by treatment group for each of the following:

- time to POAF resolution from first dose of prescription of pharmacologic intervention
- time to POAF resolution from first procedural intervention
- types of pharmacologic interventions used due to POAF

- will be further categorized by "medication of interest" (antiarrhythmics versus anticoagulants) as defined in Section 8.0 above.
- yes/no: Beta blocking agent (ATC code: C07A) withdrawn within 3 days post-surgery and no replacement (no new beta blocker prescription) within 7 days post-surgery

Other Efficacy Variables

- Percentage of participants with clinically important tachycardia in AF (defined as heart rate ≥ 100 bpm for at least 2 minutes) within 30 days post-surgery
- Percentage of participants with any occurrence of AF as defined in the primary and secondary endpoints during the first 7 days following Day 60, Day 90, Day 180, Day 270, and Day 360 visits

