15.0 Data Handling Conventions

15.1 Visit Time Windows

Table 15–1 presents the visits assigned for safety analyses and the corresponding range of treatment days (window) during which an actual visit may occur. Unless otherwise specified, efficacy parameters collected by visit (e.g., Quality of Life Outcomes) will use the same windows during which an actual visit may occur. All analyzable ePatch data collected from ePatches with a start date within the visit window will be included in the analysis for the derived visit for Days 60, 90, 180, 270, and 360.

Scheduled Visit	Study Day ^a	Time Window (Study Day Range)
Baseline	1	1
Day 2	2	2
Day 3	3	3
Day 4	4	4
Day 5	5	5
Day 6	6	[6, 10]
Day 14	14	[11, 21]
Day 30	30	[22, 45]
Day 60	60	[46, 75]
Day 90	90	[76, 135]
Day 180	180	[136, 225]
Day 270	270	[226, 315]
Day 360	360	> 315 days

Table 15–1Analysis Visit Windows

a Relative to the date of the study treatment. Day 1 = the date of the study treatment.

If the assessment date (if the assessment date is unavailable, use visit date instead) is on or after the date of the study treatment, the study day is calculated by assessment date – date of the study treatment + 1. If the assessment date is before the date of the study treatment, the study day is calculated by assessment date – date of the study treatment. Therefore, a negative day indicates a day before the start of the study treatment.

If a subject has 2 or more visits within the same window, the last visit with a non-missing value will be used for analysis. All postbaseline assessments will be considered for PCS categorization. All assessments will be included in respective listings.

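### SAP Section 10.3 times rehospitalisation from discharge but appears to censor event-free participants on a clock that starts at treatment: a small error, mended by a wording change

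*SAP*

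**What the plan says.** In SAP Section 10.3, under the rehospitalization heading, time to first all-cause rehospitalisation is "calculated as the date/time of first re-hospitalization minus the date/time of hospital discharge after surgery". For those without an event the rule is: "Participants with no rehospitalizations will be censored at their respective study exit day". The Kaplan-Meier methods of Section 10.2 apply, and with them the log-rank and Cox comparisons. Similar analyses are planned for non-arrhythmia cardiovascular and arrhythmia rehospitalisation.

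*Study exit day* has no definition of its own. Three other places bear on it:

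- Section 15.1, footnote to Table 15–1, on study day: "Relative to the date of the study treatment. Day 1 = the date of the study treatment".
- Section 9.0, on study duration: "the number of days from the date of the study treatment to the date the participant exits the study".
- Section 10.3, on interventions due to AF from Day 31 to Day 360: "Participants with no events who exit the study prior to Day 360 will be censored at their respective study exit day minus 30 days". Event-free participants who exit at Day 360 or later are censored at 330, worked out there as 360 − 30.

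The index stay is defined in Section 10.3 as "the time (days) from ICU admission date/time to the date/time of discharge from the hospital". Neither document gives an expected length. Footnote b to the Schedule of Activities (Protocol Section 1.3) says only: "Participants may remain in the hospital beyond Day 6, based on the recovery from surgery".

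**The concern.** Event times and censoring times in one survival analysis must share an origin. Here an event is timed from discharge, while the censoring rule, on the more natural reading of the SAP, gives a day number counted from treatment. The gap between the two clocks is the index stay. Event-free participants would then stay in the risk set after they had left observation, which lowers the estimated rehospitalisation rate.

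Length of stay is itself a studied outcome, so the error could in principle differ by arm. A participant who dies before discharge was never at risk of rehospitalisation. Section 10.3 says how in-hospital death enters length of stay, but not how it enters this endpoint. The literal rule would give such a participant positive post-discharge follow-up.

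**Working it through.** **1. The plan's own origin correction.** Censoring time = study exit day − study day at which the endpoint's clock starts. For the Day 31 to Day 360 endpoint this is 360 − 30 = 330, the figure the SAP prints. There *study exit day* is a day number from surgery or treatment, and the authors subtract because the clock starts later. The rehospitalisation clock also starts later, at discharge, but nothing is subtracted.

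**2. Individual participants.** Literal time = exit day. Aligned time = exit day − discharge day. Discharge days are assumptions.

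| Exit day | Discharge day | Literal | Aligned | Overstatement |
|---|---|---|---|---|
| 10 | 8 | 10 | 2 | 8 days |
| 30 | 6 | 30 | 24 | 6 days (25%) |
| 30 | 20 | 30 | 10 | 20 days (200%) |
| 60 | 6 | 60 | 54 | 6 days (11%) |
| 367 | 6 | 367 | 361 | 6 days (1.7%) |
| 367 | 20 | 367 | 347 | 20 days (5.8%) |

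The overstatement is the post-treatment stay, plus one day under the Day 1 convention. Pre-operative hospital days are not part of it.

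**3. Hand calculation for the 30-day Kaplan-Meier rate.** Assume a fixed 7-day stay, a 12% 30-day rate, and a fraction *f* exiting uniformly over the 30 days after discharge.

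- Mean extra days wrongly counted inside the 30-day window, per early exit: 7 × 23/30 + 3.5 × 7/30 = 6.18, which is 6.18/30 = 0.206 of the window.
- Inflation of the risk set: about 0.206*f*/(1 − *f*/2).
- Understatement: 0.88 × (−ln 0.88) × that inflation = 0.1125 × 0.206*f*/(1 − *f*/2).
- For *f* = 5%, 10%, 15%: 0.12, 0.24 and 0.38 points.

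**4. Simulation.**

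- Same rate and exits, arms of 110, log-normal stay with median 7 days: 0.13, 0.26 and 0.40 points for 5%, 10% and 15%. A median stay of 14 days with 10% early exits gives 0.42. A median of 7 days with the 10% spread up to Day 60 gives 0.15.
- 330 participants, mean discharge day about 9, 30-day rate about 10% or 20%, dropout of 10% or 30% spread over the year: 0.02 points (9.88% against 9.86%) to 0.10 points (18.58% against 18.48%) at day 30, and at most 0.17 by day 355. Total person-time is inflated by 2.5% to 2.9%.

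**5. Scale.** The standard error of a 12% rate with 110 participants is √(0.12 × 0.88/110) = 3.1 points. The upper figure is 0.4/3.1, about one eighth of that.

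**6. Between arms.** With 10% of exits by Day 60, a difference of 1 or 2 days in median stay moves the between-arm difference in the 30-day rate by about 0.02 or 0.04 points. It moves an unstratified log-rank z by about 0.01 or 0.02, and the 5% significance verdict changed in at most 0.4% of runs. For median stays of 7 against 14 days, with 10% exiting within 30 days of discharge, the shift is 0.42 − 0.26 = 0.16 points.

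**The case against.** The strongest reply is that *study exit day* is undefined and may mean the calendar day on which observation ends. The preceding sentences define the variable on a date/time scale from discharge, and Table 15–1 concerns visit windows. A programmer could compute exit date minus discharge date and be right. That possibility stands, so the error is not certain. It is the weaker reading, because the same section uses the same phrase as a day number and corrects its origin explicitly. Nothing elsewhere says that censoring is measured from discharge.

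The second reply is about consequence, and it largely stands. Kaplan-Meier, log-rank and Cox analyses depend on risk sets at event times. For a completer, extra days near the end of the year alter only the last risk sets, so early exits drive the error. The SAP assumes about 10% dropout in planning for completion to Day 60, so 15% leaving within 30 days of discharge is at the high end.

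A third reply concerns the endpoint's place. Time to first rehospitalisation is not among the rehospitalisation variables of Protocol Section 9.4.1.4, which are counts, binary measures and days in hospital. It is an additional SAP variable, outside the multiplicity procedure.

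Finally, leaving out participants never discharged conditions on a post-randomisation event. That is true, but they have no time origin for this variable. Reporting their number by arm keeps the condition visible.

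**Conclusion.** The inconsistency holds on the better-supported reading: events run from discharge, and censoring appears to run from treatment or surgery. Each event-free participant's follow-up is then overstated by the post-treatment index stay, in three time-to-event analyses. The size is about 0.02 to 0.4 points on the 30-day Kaplan-Meier rate. This rests on assumed stays, rehospitalisation rates and exit patterns, since the documents give no expected stay and no rehospitalisation rate.

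A reader might infer that rehospitalisation is materially understated throughout, or that the treatment comparison is distorted because stay is an outcome. The documents do not support either. The percentages and counts within 30 days of discharge and 60 days of surgery do not use this censoring rule. No expected difference in stay between arms is stated, and differences of 1 or 2 days barely move the comparison. This is a minor correction.

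**What to change.** In SAP Section 10.3, replace the censoring sentence with one stating that event-free participants are censored at study exit date/time minus the date/time of hospital discharge after surgery, for all three rehospitalisation types. Add that participants who die or exit before discharge have no time origin and do not enter this time-to-event analysis, and report their number by treatment group.

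The cost is two sentences and a small change to the derivation. Discharge and exit dates are already needed for length of stay and study duration, so no new data are required. The change does not address death after discharge, which stays outside this correction.
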